## LIST OF ABBREVIATIONS

Abbreviation	Explanation
3-OMD	3-O-methyldopa
ADR	Adverse Drug Reaction
AE	Adverse Event
ALT	alanine transaminase
AST	aspartate transaminase
AUC	Area Under the Curve
BK	Bradykinesia Score
BMI	Body Mass Index
CD	Carbidopa
CI	Confidence Interval
СК	creatine kinase
COMT	Cathecol-O-methyltransferase
COV	Coefficient of Variation
CSP	Clinical Study Protocol
DHPA	3,4-dihydroxypheylacetone
DK	Dyskinesia Score
EC	Ethics Committee
ECG	Electrocardiogram
eCRF	Electronic Case Report From
EMA	European Medicines Agency
EU	European Union
FDS	Fluctuation Score
GCP	Good Clinical Practice
GLP	Good Laboratory Practice
GMP	Good Manufacturing Practice
H&Y	Hoehn and Yahr
i.v.	Intravenous
IB	Investigator's Brochure
ICF	Informed Consent Form
ISF	Investigator's Study File
IVO	The Health and Social Care Inspectorate
LCIG	Levodopa-Carbidopa Intestinal Gel
LD	Levodopa
LLOQ	Lower Limit Of Quantification
MPA	Medicinal Products Agency
PD	Parkinson's Disease
PE	Polyethylene
PK	Pharmacokinetics
PKG	Parkinson's KinetiGraph
PTF	Peak-through fluctuation
PTT	Percent Time with Tremor
RBC	Red Blood Cell
	Subcutaneous
s.c. SAE	Subculateous Serious Adverse Event
SD	Standard Deviation
SUSAR	Suspected Unexpected Serious Adverse Reaction
TRS	Treatment Response Scale
UPDRS	Unified Parkinson's Disease Rating Scale
VAS	Visual Analogue Scale
WBC	White Blood Cell

## SYNOPSIS

Title: Levodopa pharmacokinetics in patients with Parkinson's disease and symptom fluctuation: A phase I, open-label, randomized, multicentre, crossover study comparing intravenous and subcutaneous Infudopa with intestinal Duodopa

### Study site(s) and number of subjects planned

Approximately 6 sites in Sweden will participate in the study. Five interim patients were completed 2nd Quarter 2018. Approximately 22 more patients aged 30 and above are to be enrolled in this study.

Study period		Phase of development
Date of first patient enrolled	2nd Quarter 2018	I
Estimated date of last patient completed	4th Quarter 2019	

## Study design

IPO-001 is a prospective, randomized, 3-period cross-over, open-label multicentre trial comparing intravenous and subcutaneous Infudopa with intestinal Duodopa. The trial includes patients with Parkinson's disease who are on Duodopa treatment because of severe on-off manifestation when on oral levodopa. The patients will be identified and recruited at neurology clinics at university hospital clinical sites in Sweden, and travel from their living location to a clinical phase I site with full Good Clinical Practice (GCP) standard at the Sahlgrenska University Hospital in Gothenburg for the three treatment visits.

The subjects will be assessed at the phase I study clinic, where they during one treatment visit will receive Duodopa at optimal dosage for 16 hours, during another treatment visit will receive i.v. Infudopa at a rate estimated to yield corresponding serum levels of levodopa for the same duration, and at a third treatment visit will again receive the corresponding amount of levodopa but in the form of s.c. Infudopa. The study will hence have a cross-over design with a minimum of three days on Duodopa between the different treatment visits, where the order of treatments will be non-blinded but randomized.

Blood samples will be drawn according to a set schedule during the treatment visits, and subjects will be monitored for safety throughout the study, with focus on the local tolerability at the injection sites of i.v. and s.c. administration.

The duration of subject participation in the study is expected to be around 3-4 months from screening to final follow-up (with variation depending on subject's availability between treatment visits), and the subject will be on study treatment for in total 3 days (3x16 hours).

#### **Objectives**

Primary objective is to:

• Demonstrate that Infudopa i.v. and s.c. yield steady state plasma concentrations of levodopa that are equivalent with those of Duodopa, and that the variability in plasma concentrations during the dosage interval is non-inferior to that obtained with Duodopa.

Secondary objectives are to:

- Evaluate the safety of the products with special focus on the local tolerability at the injection sites of i.v. and s.c. administration.
- Establish the bioavailability of levodopa and carbidopa given s.c. and as Duodopa compared to the i.v. administration.
- Compare other pharmacokinetic variables as well as motor function during treatment with s.c. and i.v. Infudopa versus Duodopa.

#### Investigational product, dosage and mode of administration

Infudopa will be supplied in three different bottles: 1. Infudopa Active containing 20 mg/mL levodopa and 2.5 mg/mL carbidopa, 2. Infudopa Buffer IntraV, and 3. Infudopa Buffer SubC, the two latter with no active ingredients. Product 1 will be combined with product 2 for i.v. infusion, and product 1 with product 3 for s.c. infusion. After online mixing by two infusion pumps, Infudopa will contain 10 mg/mL levodopa and 1.25 mg/mL carbidopa. Each single dose treatment in the 3 dose groups below will be given during 16 h.

Dosing will be based on the patient's *regular day time hourly dose-requirement of Duodopa*. This consists of the regular continuous Duodopa dose (mg) plus the average accumulated daily extradoses (mg) divided by the regular daily infusion time (h). The morning Duodopa bolus dose is for the study set to 110% of the *regular day time hourly dose-requirement of Duodopa*. Consequently the *pre-study daily Duodopa dose* is for this study defined as:

The regular day time hourly dose-requirement  $\times$  (16 h – morning bolus infusion time h) + 110% of the regular day time hourly dose-requirement of Duodopa.

**Dose group 1.** Infudopa i.v. infusion will be given through an indwelling catheter placed in the arm. The total Infudopa i.v. dose will be 81% of the subject's individual *pre-study daily Duodopa dose*. Infudopa i.v. will be administered as a morning bolus dose followed by continuous i.v. infusion up to 16 h. The morning bolus dose will be 110% of the hourly continuous dose. The morning dose will not exceed 24 mL after mixing, corresponding to 240 mg levodopa. The expected 16-h levodopa dosage will be in total 492 to 2900 mg. The maximum daily dose levodopa during i.v. administration is not allowed to exceed 3240 mg (equal to 81% of the maximum allowed daily dosage for Duodopa that is 4000 mg).

**Dose group 2.** A suitable split 2-needle infusion set will be placed laterally on the abdomen for the s.c. infusion of Infudopa. The total Infudopa s.c. dose will be 86% of the *pre-study daily Duodopa dose*. Infudopa s.c. will be administered as a morning bolus dose followed by continuous s.c. infusion up to 16 h. The morning bolus dose will be 155% of the hourly continuous dose. The morning dose will not exceed 30 mL after mixing, corresponding to 300 mg levodopa. The expected 16-h levodopa dosage will be in total 496 to 2950 mg. The maximum daily dose levodopa during s.c. administration is not allowed to exceed 3440 mg (equal to 86% of the maximum allowed daily dosage for Duodopa that is 4000 mg).

**Dose group 3.** Duodopa will be supplied in cassettes containing a gel with 20 mg/mL levodopa and 5 mg/mL carbidopa monohydrate, and be administered directly to the proximal small intestine via a PEG-J tube connected to a portable infusion pump. In dose group 3 the patient will receive the *pre-study daily Duodopa dose* administered as a morning bolus dose (110% of the continuous hourly dose) followed by continuous infusion up to 16 h. The morning dose will not exceed 15 mL, corresponding to 300 mg levodopa. The expected 16-h levodopa dosage will be in total 600 to 3160 mg. The maximum daily dose levodopa is not allowed to exceed 4000 mg.

## Statistical methods

Statistical assessments of dosage normalized levodopa AUC0-inf, AUC0-last, AUC0-16, AUC0-2, AUC2-16, and AUC8-16 by analysis of variance (ANOVA) will be made on the logarithmic values, with back-transformation to nominal values of point estimates and confidence interval (CI). These variables will also be tested with dosage un-normalized values. The terms to be used in the ANOVA model will be sequence, patient within sequence, period, and formulation (i.v. or s.c. Infudopa and Duodopa; test and reference, respectively).

The statistical method for testing relative dosage normalized levodopa bioavailability will be based on the 90% CI for the ratio of the population means (test/reference). These statistical tests will also be done with dosage un-normalized values. The acceptance range for AUC ratio of the 90% CI for levodopa will be 0.80 to 1.25. These tests will be performed for Infudopa i.v. or Infudopa s.c. vs. Duodopa comparison.

The COV (coefficient of variation or % standard deviation; SD) will be calculated for each individual for plasma concentration between 2 and 16 h by dividing the SD for each individual curve with the mean value of plasma concentration between 2 and 16 h. The mean value of plasma concentration will be calculated for each curve as AUC2-16/14. Basic statistics for the COV will then be calculated per treatment group. The one-sided 90% CI of the intersubject COV will be calculated for Treatment 1 (i.v.) and Treatment 2 (s.c.) vs. Treatment 3 (Duodopa; reference) comparison, and for Treatment 1 (i.v. reference) vs. Treatment 2 (s.c.). It will also be tested with paired t-tests if there are significant differences in intersubject COV between treatments (i.v. vs. Duodopa, s.c. vs. i.v., and s.c. vs. Duodopa).

The level of significance will be p=0.05.

Clinical Study Protocol	Study code:	IPO-001
	Version No:	5.1
	Date:	26 MARCH
		2019

Safety will be summarized with the standard set of AE summary tables, and descriptive summary statistics of vital signs by visit and change from baseline. Local tolerability will be presented with descriptive summary statistics by visit and change from baseline.

## 1. INTRODUCTION

## 1.1. Background and rationale for conducting the study

The critical importance of the brain neurotransmitter dopamine for the regulation of locomotion was first described by the 2000 Nobel laureate Arvid Carlsson. In patients with Parkinson's disease (PD), the characteristic motor symptoms, i.e., slowness of movement (bradykinesia), tremor and rigidity, are consequences of the progressive degeneration of neurons containing and releasing dopamine.

As the result of Carlsson's seminal discovery that administration of levodopa – a precursor to dopamine that (unlike dopamine) passes the blood brain barrier – restored locomotion in animals rendered immobile due to dopamine depletion, neurologist George Cotzias introduced per oral administration of levodopa as a treatment for Parkinson's disease in the late 60's. As yet, this remains the unchallenged first-line treatment of this disabling condition (Carlsson, 2002).

Levodopa is usually co-administered with a peripherally acting compound that inhibits the enzyme levodopa decarboxylase, which converts levodopa to dopamine. By reducing the peripheral decarboxylation of levodopa, the amount of levodopa that reach the brain is hereby enhanced and the side effects caused by dopamine outside of the brain minimized. One commonly used such peripheral levodopa decarboxylase inhibitor is carbidopa.

During the first few years of treatment with levodopa, patients usually experience symptom reductions that last for 6 hours or longer after drug intake. With time, however, symptom reduction to an increasing extent reflects the short half-life of levodopa in serum (60-90 minutes). Some patients also respond with drug-induced dyskinesias. The human suffering and societal costs caused by this unpredictable and disabling condition, usually referred to as the on-off syndrome, are immense (Lökk et al, 2012).

Inpatient studies, in which levodopa has been administered intravenously, have demonstrated that the on-off syndrome is partly caused by the marked variation in serum levodopa levels following per oral administration. Thus, when patients experiencing marked on-off symptoms on oral treatment are instead exposed to an infusion causing stable serum levels of levodopa, the fluctuations in motor function to a large extent disappear (Shoulson et al, 1975, and Quinn et al, 1984).

A logical approach to the on-off problem in outpatients would thus be to administer levodopa by a route of administration causing stable serum levels either by means of continuous subcutaneous administration (as used e.g. for insulin in patients with diabetes) or by continuous intravenous administration (as used e.g. for administration of chemotherapy to patients with cancer) using an infusion pump. However, no such formulation is yet approved by regulatory bodies for market access, the major obstacle having been to produce a levodopa solution with sufficient concentration and/or stability.

Levodopa–carbidopa intestinal gel (LCIG) is a carboxymethylcellulose aqueous gel delivered directly to the proximal small intestine via a percutaneous endoscopic gastrojejunostomy (PEG-J) tube connected to a portable infusion pump. Infusion of LCIG in the jejunum bypasses gastric emptying, helping to avoid the fluctuation in plasma levodopa levels. Daytime infusion of LCIG has demonstrated significantly improved motor symptoms and quality-of-life measures in advanced PD

	Study code:	IPO-001
Clinical Study Protocol	Version No:	5.1
	Date:	26 MARCH
		2019

patients compared to standard oral therapy (Wirdefeldt et al 2016). This formulation (under the name Duodopa®) has been approved in the European Union (EU) and several other countries on the indication "Treatment of advanced levodopa-responsive Parkinson's disease with severe motor fluctuations and hyper-/dyskinesia when available combinations of Parkinson medicinal products have not given satisfactory results".

However, while clearly confirming that an even administration of levodopa is of considerable benefit to Parkinson patients with on-off symptomatology, the LCIG approach is marred by the need for surgery (for the insertion of the intestinal tube) and various possible complications following this, as well as by side effects such as abdominal pain. There are also reports of weight loss and polyneuropathy that are suspected to result from the intestinal continuous administration of levodopa-carbidopa gel. No doubt, much would be gained if the stable serum levels of levodopa produced by LCIG could instead be obtained by means of an s.c. pump not requiring surgery.

A neurologist at Linköping University Hospital ([name]) succeeded in producing a physiologically acceptable levodopa solution in a concentration allowing for a continuous intravenous (i.v.) or subcutaneous (s.c.) administration of therapeutic doses to humans. Early experience of this strategy at the Linköping University Hospital confirms that both i.v. and s.c. administration of this solution results in stable serum levodopa levels and markedly improved motor functioning ([name] and co-workers, unpublished).

Based on the early work of [name], researchers at Dizlin Medical Design AB, Pharm Assist Sweden AB, and University of Gothenburg, together with [name], and in collaboration with Recipharm AB, have now produced a modified version of the original solution, Infudopa, containing even higher levels of levodopa as well as carbidopa. The aim of the present study will be to compare the pharmacokinetic profile of Infudopa administered i.v. and s.c. with that of LCIG administered enterally in parkinsonian patients with on-off complications, the tested hypothesis being that s.c. and i.v. administration of Infudopa will result in serum levels of levodopa at least as stable as those obtained by LCIG at clinically effective dosage. By showing this, we hope to expedite the clinical introduction of s.c. Infudopa as an alternative to LCIG for outpatients with Parkinson's disease with on-off symptoms and/or of the introduction of i.v. Infudopa for the treatment of inpatients requiring a stabilisation of serum levolopa levels in order to be eligible for surgery.

## 1.2. Rationale for study design

The aim of this study is to alleviate the considerable human and societal burden caused by late stage Parkinson's disease with on-off symptomatology by facilitating a prompt clinical introduction of s.c. (and/or i.v.) administration of Infudopa in Sweden and other countries. To this end, a moderately but adequately sized multi-centre study will be undertaken with the aim of confirming that i.v. or s.c. administration of Infudopa causes as stable serum levels of levodopa as does Duodopa, administrated enterally, which will serve as a control treatment. The study will also monitor the safety of these administrations, with focus on the local tolerability at the administration site, both during stay at the phase I ward and at follow-up.

Since the active ingredients of Infudopa are the same as in Duodopa, i.e. levodopa and carbidopa, and since it is already well established that the stable serum levels of levodopa obtained by

Clinical Study Protocol	Study code:	IPO-001
	Version No:	5.1
	Date:	26 MARCH 2019

Duodopa is of marked benefit for patients with the on-off syndrome, showing that similar serum levels as those resulting from Duodopa may be obtained also by s.c. Infudopa might be sufficient for introducing s.c. Infudopa as a novel treatment of Parkinson's disease by means of a so-called hybrid application (EU regulation 726/2004). The primary aim of the planned study is hence not to show efficacy of Infudopa, which would be a much more costly endeavour, but to confirm that Infudopa is equal to Duodopa in causing stable serum levodopa levels at comparable steady-state levels of levodopa. Adverse effects during the one-day treatment and at follow-up will be recorded as well. For exploratory purposes, motor function during the one-day treatment with Dudopa. i.v. Infudopa, and s.c. Infudopa, respectively, will also be assessed. While it will not be possible to blind the study, motor function will be assessed by objectives measures, i.e. by video recording rated by an observer blind to treatment in combination with automatic measurement of motor function using a wrist worn device (Parkinson's KinetiGraph) (Grifftiths et al, 2012).

Short-term injections or infusions of i.v. Infudopa would be highly valuable in clinical situations when oral levodopa treatment temporarily is not working. Of note is that many patients with disabling late stage Parkinson's disease with on-off symptomatology are at present denied surgery for various disorders since they are not believed to be able to cope with the intervention and/or rehabilitation because of their poor motor condition. While the main purpose of this study, as discussed above, is to expedite the process of introducing long-term s.c. Infudopa for outpatients with the on-off syndrome, the introduction of i.v. Infudopa to in-patients may also meet a considerable unmet medical need by making it possible to conduct surgery, sometimes lifesaving, on this group of patients. Such treatment can be short-term and based individually on the patients need pre- intra- or postoperatively and can be given as slow injections of also low dosages. If successful, the trial presented in this application may thus make it possible to introduce this strategy to surgery-warranting patients with Parkinson's disease in Sweden and elsewhere shortly. In addition, in case unforeseen problems should arise regarding the s.c. administration, i.v. Infudopa administered at a continuous basis by means of a subclavian port-a-cath may turn out to be a feasible strategy for outpatients.

Based on statistical power analyses of primary efficacy variables (section 8.1), the required number of subjects is estimated to be 24. It is suggested to include 28 subjects into the study in order to compensate for 4 possible drop-outs.

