There is no reason to believe that Infudopa would exhibit any additional systemic adverse reactions than those described for other levodopa/carbidopa products, as summarised in the product information for Duodopa (see Investigator's Brochure). Duodenal administration of Duodopa has, however, a high risk of device- and procedure-related adverse reactions, such as postoperative wound infection, excessive granulation tissue, and incision site erythema, each reaction affecting more than 10% of patients (see Investigator's Brochure).

There is a potential risk of local adverse reactions at the administration site following Infudopa, however, local tolerance study in rabbits indicate that this risk should be low, and the reaction only short-term and not severe. However, the interim analysis of 5 patients showed that s.c. administration was associated with hematoma and transient and moderate pain or discomfort. Based on literature data, it was concluded that this was most likely due to the relatively high osmolarity caused by the high citrate concentration of the solution. Thus, when the trial starts again, a new buffer composition named Infudopa Buffer SubC, with a citrate concentration of only 20% of the previous one, will be used for the s.c. administration.

The half-life in plasma is short for levodopa, meaning that a lowering in pump rates following all routes of studied administration will quickly adjust down the levels of levodopa in plasma should, for example, dyskinesia occur. The clinical study is conducted at a phase I centre with intense monitoring of the patients that further reduces the risks. Please also refer to section 6.2 in the clinical study protocol for study dose and study design rationales. Data from the interim analysis have also given information allowing a fine tuning of the dosages.

When the study starts again, there will be a new interim analysis of pharmacokinetics (PK) and safety data after 4 of 18 (or 22 considering also possible compensatory patients) completed patients, after which a monitoring committee will meet to discuss the results and conclude if the study should continue, be modified with respect to design or discontinued. Evaluation will include blood PK samples, inspection of local dermal area/scoring including photos, and adverse events.

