## 3. STUDY DESIGN AND PROCEDURES

## 3.1. Overall study design and flow chart

This is a prospective, randomized, 3-period cross-over, open-label multicentre trial. Patients fulfilling all of the inclusion and none of the exclusion criteria will be randomized to one of the three treatment arms. There have been 5 interim patients already studied. Enrolment upon restart of the study will be continued until the required sample size is achieved (18 subjects in total entering the second part of the study, giving in total 23 subjects in the study). Once informed consent is

[figure not shown]
	Study code:	IPO-001
Clinical Study Protocol	Version No:	5.1
	Date:	26 MARCH 2019

obtained, screening data will be collected to determine each patient's eligibility for study participation.

The duration of subject participation in the study is expected to be around 3-4 months from screening to final follow-up (with variation depending on subject's availability between treatment visits), and the subject will be on study treatment for in total 3 days.

Patients with Parkinson's disease who are on Duodopa treatment because of severe on- off manifestation when on oral levodopa will be identified and recruited by experienced neurologists at neurology clinics at university hospital clinical sites in Sweden. Patients will travel from their living location to a clinical phase I site with full Good Clinical Practice (GCP) standard at the Sahlgrenska University Hospital in Gothenburg for the three treatment visits.

The subjects will be assessed at the phase I study clinic, where they during one treatment visit will receive Duodopa at optimal dosage for 16 hours, during another treatment visit will receive i.v. Infudopa at a concentration estimated to yield corresponding serum levels of levodopa for the same duration, and at a third treatment visit will again receive the corresponding amount of levodopa but in the form of s.c. Infudopa. The study will hence have a cross-over design with a minimum of three days on Duodopa between the different treatment visits, where the order of treatments will be non-blinded but randomized.

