## 4.4. Subject enrolment and randomization

Subject eligibility will be established before *enrolment*. Subjects will be *enrolled and randomized* strictly sequentially, as subjects are eligible *for randomization*. If a subject discontinues from the study, the subject number will not be reused, and the subject will not be allowed to re-enter the study.

Identified potential study subjects will be given thorough information regarding the study, both orally and in writing, by a physician. After the subject has been given the opportunity to ask any question regarding the study they will be asked to consent to study participation. If they do, they will sign the informed consent form.

At screening (before randomization): subjects will be assigned a unique subject identification (enrolment number).

At randomization, all eligible subjects will be given a randomization number that assigns them to one of the treatment groups. The randomization numbers are sequentially allocated to the subjects in the order of randomization. Each subject will receive only that treatment regimen which is labelled with the randomization number allocated to him/her.

If the subject fails to be randomized for any reason, the subject's identification and the reason for not being randomized will be entered into the eCRF. Note: The enrolment number is different from the randomization number.

Randomization will be performed with random assignment of treatment groups in the specified ratio of 1:1:1.

Subjects discontinuing treatment prematurely will not be replaced.

According to the recommendations given in the ICH E9 Guideline "Statistical Principles for Clinical Trials" (CPMP, 1998), the used block length is specified in a separate document, which is withheld from the study centre.

	Study code:	IPO-001	
Clinical Study Protocol	Version No:	5.1	
	Date:	26 MARCH 2019	

Subjects who fail to meet the eligibility criteria should not, under any circumstances, be enrolled or receive study medication. There can be no exceptions to this rule. Subjects who are enrolled, but subsequently found not to meet all the eligibility criteria must not be randomized or initiated on treatment, and must be withdrawn from the study.

Where a subject does not meet all the eligibility criteria but is randomized in error, or incorrectly started on treatment, the subject should be discontinued as soon as the error or incorrectness is evident, and returned to pre-study treatment, i.e. Duodopa.

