#### Table 4. Product identity

#### 5.1.1. Doses and treatment regimens

All dosing during the study will be based on the patient's *regular day time hourly dose-requirement of Duodopa*. This consists of the regular continuous Duodopa dose (mg), plus the average accumulated daily extradoses (mg) divided by the regular daily infusion time (h). The morning Duodopa bolus dose is for the study set to 110% of the *regular day time hourly dose-requirement of Duodopa*. Consequently the *pre-study daily Duodopa dose* is for this study defined as:

The regular day time hourly dose-requirement  $\times$  (16 h – morning bolus infusion time h) + 110% of the regular day time hourly dose-requirement of Duodopa.

The total dose per day will be the sum of two components: morning bolus dose, and continuous (maintenance) dose given over a 16-h period. The combined i.v. infusion of Infudopa Active with Infudopa Buffer IntraV will be named Infudopa IntraV, and the combined s.c. infusion of Infudopa Active with Infudopa Buffer SubC will be named Infudopa SubC. In the following text doses and treatments apply to subjects in the second phase of the study (n=18). Before the start of this phase, it was decided that the bolus doses should be determined by a fixed percentage of the continuous hourly dose. The percentage chosen was for Infudopa IntraV 110%, for Infudopa SubC 155%, and for LCIG 110%. If clinically justified in the individual patient, the bolus dose may be adjusted, maintaining the relation 1 : 1.4 : 1 between the bolus doses for the different administration modes i.v : s.c : intestinal. The total dose is adjusted for the relative bioavailability based on AUC during the 0-16 h dosage interval vs. LCIG that was found in the interim study (ratio LCIG/Infudopa IntraV = 0.81; ratio LCIG/Infudopa SubC = 0.86).

Clinical Study Protocol		Study code:	IPO-001
	Clinical Study Protocol	Version No:	5.1
		Date:	26 MARCH 2019

Treatments will comprise the following therapy, where treatment 1 and 2 are considered investigational, and treatment 3 reference therapy:

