# 8. STATISTICS

## 8.1. Sample size calculation

Sample size determinations are based on the primary pharmacokinetic variable from a similar study (Nyholm et al, 2013) regarding 16-hour intestinal infusion of Dudopa in advanced Parkinson's disease patients. Data from the 5 interim analysis patients are also used. A standard t-test model with continuity correction has been used (Microsoft Excel program, Pharm Assist Sweden AB). Z-alpha level was 1.96 and Z-beta level was 0.84 for equivalence testing of 90% CI of 0.80 to 1.25, and Z-alpha level was 1.65 and Z-beta level was 0.84 for non-inferiority testing of 90% CI of 0.80 to 1.25.

The test suggests that 14 subjects are appropriate for the test of dose-normalized AUC 0 to infinity of levodopa. This number of subjects is valid both based on the Nyholm et al. 2013 data for LCIG (COV 24.5%), and the data in the interim study (COV 17.0% allowing as a safety margin for a 40% higher COV, 23.8%, giving n=14).

For the non-inferiority test of intersubject coefficient of variation (COV) the sample size estimation suggests 18 subjects to be included.

Based both on the levodopa dose-adjusted AUC 0 to infinity and the intersubject COV it is planned that 22 subjects will be recruited to the study, also allowing for 4 drop-outs.

Clinical Study Protocol	Study code:	IPO-001
	Version No:	5.1
	Date:	26 MARCH 2019

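### Section 1.2 gives a sample size (24/28) that section 8.1 does not contain, and section 3.1 stops enrolment at 18 entrants, dropping 8.1's allowance for 4 drop-outs

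*Protocol*

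**What the plan says.** The protocol (version 5.1) states the size of the study in several places.

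- **Section 1.2** refers to section 8.1 as its source and says "the required number of subjects is estimated to be 24. It is suggested to include 28 subjects into the study", the difference being 4 possible drop-outs.
- **Section 8.1** arrives at 14 subjects for dose-normalised AUC from zero to infinity. For the non-inferiority test of the COV, "the sample size estimation suggests 18 subjects to be included". It concludes that "it is planned that 22 subjects will be recruited to the study, also allowing for 4 drop-outs".
- **Section 3.1** lets enrolment run until the required number is reached and defines that number as "18 subjects in total entering the second part of the study, giving in total 23 subjects in the study".
- **The synopsis** counts five completed interim patients and then says "Approximately 22 more patients aged 30 and above are to be enrolled in this study".
- **Section 1.4** places the next interim analysis "after 4 of 18 (or 22 considering also possible compensatory patients) completed patients".
- **Section 4.4** says "Subjects discontinuing treatment prematurely will not be replaced".

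Non-inferior variability is in the primary objective (section 2.1), and the COV is listed among the primary variables (section 6.1).

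**The concern.** Two statements do not fit the sample-size section. Section 1.2 attributes to 8.1 figures that are not there. Section 3.1 takes the 18 that 8.1 needs for the COV test and makes it the number that enters, so the 4 that 8.1 adds on top are lost.

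The second matters more, because section 3.1 is where the protocol says when recruitment ends. A team following it stops at 18 new patients. A team following the synopsis stops at about 22. With no replacement under section 4.4, stopping at 18 leaves nothing in reserve among the new patients. Once enrolment has closed, the gap can be filled only by reopening it.

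A related point is left open: whether the first 5 patients count. Section 8.1 speaks of 22 recruited to the study, while the synopsis counts 22 beyond the 5. The 5 had an earlier s.c. buffer (the new one has 20% of its citrate concentration, section 1.4) and s.c. dosing based on a different bioavailability assumption (section 1.3). The protocol does not say whether their data count toward the 18.

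**Working it through.** **1. Reproduce 8.1.** Inputs from section 8.1: z-values 1.96 and 0.84 for equivalence, limits 0.80 to 1.25, COV 24.5% (earlier study of Duodopa infusion) or 23.8% (interim 17.0% × 1.4). The section names a t-test model with a correction but prints no formula. This one, inferred, reproduces its result:

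n = ((z_alpha + z_beta) × COV / 0.20)² + z_alpha²/2

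- COV 24.5%: (2.80 × 0.245 / 0.20)² + 1.92 = 11.76 + 1.92 = 13.69, rounded up to 14.
- COV 23.8%: (2.80 × 0.238 / 0.20)² + 1.92 = 11.10 + 1.92 = 13.02, rounded up to 14.

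Both match the stated 14. Recruitment: max(14, 18) + 4 = 22, also as stated. The 18 for the COV test cannot be recomputed, because 8.1 gives no SD for it.

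**2. Compare the targets.**

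- Section 1.2: 24 + 4 = 28. Neither number follows from 8.1.
- Section 8.1: 18 + 4 = 22.
- Section 3.1: 18 entering, plus 5 earlier patients = 23.
- Synopsis: 5 + 22 = 27.

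**3. Patients left after the protocol's own 4 drop-outs, all taken as non-evaluable.**

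| Reading | Start | Left |
|---|---|---|
| 3.1, new patients only | 18 | 14 |
| 3.1, first 5 pooled | 23 | 19 |
| 8.1 and synopsis, 22 new | 22 | 18 |
| 8.1 if the 22 include the first 5, new patients only | 17 | 13 |
| 1.2 | 28 | 24 |

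**4. Power of the COV test.** Assumption: 18 subjects give exactly 80% power with 8.1's z-values 1.65 and 0.84, under the form of formula found in step 1. Then

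margin/SD = (1.65 + 0.84) / √(18 − 1.65²/2) = 2.49 / √16.64 = 0.610

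and power at n is Φ(0.610 × √(n − 1.36) − 1.65). Only the ratio enters; with a margin of 0.20 it corresponds to an SD of about 0.33.

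The range covers back-solving with or without the correction term, taking 18 as exact or as just rounded up from 17, and a normal or a paired-t calculation.

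| n | Power | Range |
|---|---|---|
| 13 | 67% | 64–70% |
| 14 | 70% | 67–73% |
| 17 | 78% | 75–80% |
| 18 | 80% (by assumption) | 77–82% |
| 19 | 82% | 79–84% |

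The AUC test needs 14 and would still have 14, so the loss falls on the COV test.

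**The case against.** The strongest reply is that most of the protocol describes one coherent plan. The synopsis, section 1.4 and section 8.1 all fit 18 needed and 22 recruited, so 18 and 22 are not rival targets. That stands. The errors are 24/28 in section 1.2 and the use of 18 as the number entering in section 3.1. The n=18 in section 5.1.1 only says which subjects the dosing text covers and is not an enrolment rule.

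A reader might also infer that section 4.4 (no replacement) contradicts section 1.4 (compensatory patients). The text does not establish this. The step from 18 to 22 in 1.4 equals 8.1's allowance of 4, and recruiting 4 extra from the outset is compatible with not replacing individuals. The wording should be made clear, but a contradiction is not shown.

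Finally, a reader might infer that following section 3.1 necessarily leaves the COV test underpowered. It does not:

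- With no drop-outs, 18 is met.
- If the first 5 are pooled, 23 − 4 = 19 also meets it, and the protocol does not exclude them.
- Section 8.3 keeps in the PK population anyone with analysable data from at least two treatment visits. A patient who leaves after the s.c. and Duodopa visits therefore still contributes to that comparison.

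The power figure itself is not the protocol's, since 8.1 gives no SD for the COV. These points make the shortfall conditional. They do not remove the wrong figures in 1.2 or the missing allowance in 3.1.

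**Conclusion.** The point holds in a limited form. Section 1.2 misstates the section that it cites, and section 3.1 sets an end of enrolment that omits the planned allowance of 4 and disagrees with the synopsis. Both are plain from the text.

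The consequence is a possible loss, not a certain one. It requires that section 3.1 is followed over the synopsis and 8.1, that some drop-outs are non-evaluable for the comparison, and that the first 5 patients do not count. Each such drop-out then takes the COV test one further below 18. At the planned 4, 14 remain and power is about 70% (67 to 73%) instead of 80%, on the back-solved SD. With 22 new patients and 4 drop-outs, 18 remain, as 8.1 intends.

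**What to change.** - **Section 1.2:** replace 24 and 28 with 18 evaluable and 22 recruited.
- **Section 3.1:** let enrolment continue to 22 entering the second part, in order to obtain 18 evaluable, and correct the total accordingly.
- **Sections 8.1 and 3.1:** state whether the first 5 patients are included in the 22 and whether they count toward the 18. The synopsis counts the 22 on top of the 5; section 8.1 should say so too, or the sponsor should state the other reading everywhere. Whether to pool the 5 is the sponsor's decision, given the changed s.c. buffer and dosing.
- **Sections 1.4 and 4.4:** say that the extra 4 are the drop-out allowance recruited from the outset, so that no replacement of individuals is implied.

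The cost is a wording amendment. No patients are needed beyond the 22 already planned in the synopsis and section 8.1.
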